6. SPECIFIC AIMS

Aim 1: To determine feasibility of training lay-personnel in the performance of ACT for aPLWH to inform future implementation. Many HIV clinics employ non-medical staff such as case managers and health educators who if trained to provide ACT would expand of ACT access to aPLWH. We will train a substance abuse counselor and case manager in ACT to inform the feasibility of future ACT scale-up efforts.

Aim 2: To conduct an uncontrolled study of group ACT for chronic pain in aPLWH to inform adaption of ACT for aPLWH. Ten aPLWH will participate in 6 weekly sessions of group-administered ACT. Informed by the Method for Program Adaption through Community Engagement (MPACE) Model, I will synthesize and present data from questionnaires, participant feedback and end of study focus group to a steering committee for adaption recommendations(1). These procedures can occur in person or remotely. We will statistically evaluate the process and compare group cohesion scores between persons who attend live and remotely.

Aim 3: To conduct a controlled, two-group, pilot randomized trial of adapted ACT for aPLWH as compared to group education. Forty aPLWH with chronic non-cancer pain will be randomized to 6 weeks of group ACT or group education. Participants will undergo evaluations of acceptability as the primary outcome as recommended by the ORBIT model(2). Additional evaluations will include self-reported pain severity and interference, outcomes of physical performance, and quality of life (3, 4).

The long-term goal of this research is to develop an effective non-pharmacologic intervention to improve chronic pain in aPLWH that can be feasibly implemented on a large scale in HIV clinics. This research, in conjunction with the activities proposed in the Professional Development Plan, will help launch my career as a future leader in aging-focused research.

In order to address these hypotheses and aims, human subjects are required.

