For AIM 2: Uncontrolled group ACT for Chronic Pain in aPLWH: Ten aPLWH will be recruited for 6 weeks of 2-hour group ACT using previously developed ACT for chronic pain manuals developed for therapists and clients by [name] (Table 2). All sessions will be audio recorded for future analysis. Following each session participants will undergo recorded 10 minute short interview on aspects of the class they liked most and least. These surveys will employ open-ended questions about program content. Participants will undergo baseline demographics and questionnaires about pain and psychosocial co-morbidities (see assessments) to inform generation of open-ended questions and development of a focus group guide. Data from participant feedback and questionnaires will be presented to the steering committee to assist with development of the focus group guide. Participants will complete follow up questionnaires and guided interview questions 3, 6, and 12 months after completion of the group sessions to assess long-term use of ACT.

Table 2: Session Intervention Content

Session	ACT	Take Charge of Your Pain
1	Letting Go	Things to Know about Pain
2	Values	Relaxation
3	Cognitive Defusion	Imagery
4	Mindfulness	Activity Pacing
5	Commitment	Sleep Tips
6	Moving Forward	Dealing with Pain Flare-Ups
7	Practice/review	Review
8	Practice/review	Review

For AIM 2 Adaption of ACT: Following the final group session, a 1-3 hour long focus group will be performed to obtain suggestions for program modification. The focus group will be audiotaped and responses transcribed, categorized and summarized and distributed to members of the study's steering committee which will then meet to review and adjudicate suggested ACT adaptations. Adoptions will

be incorporated into new therapist and client manuals and further training will be provided to ACT therapists for the performance of adapted ACT.

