For AIM 3 Acceptability and Feasibility of Adapted ACT Intervention: Forty persons will be randomized to either group adapted ACT or group education. In anticipation of ~15% early discontinuation or lost to follow up, we plan to recruit 50 participants overall. All sessions will be audio recorded for future analysis. Adapted ACT will be provided by ACT therapists in weekly 2-hour group (8-10 persons per group) sessions for the 6 weeks of the intervention and will include brief review of at-home practice assignments, introduction of new material and end with assigned at-home practice exercises. Participants randomized to control will also participate in 2-hour 6 weeks group sessions (8-10 persons) using the “Take Charge of Your Pain” handbook developed by Investigators at the Weill-Cornell Translational Research Institute for Pain in Later Life (Table 2). All sessions will be audio recorded for future analysis. Study participants will complete assessments at baseline, week 3 (midpoint) and week 6 (endpoint). Following completion of study we will assess for persistence of ACT activities and practices by a short telephone follow up. Participants may come to the AVRC for an in person discussion but this will not receive monetary compensation.

Remote Engagement of Study Participants

To ensure safety of participants (who are all older adults with the co-morbidity of HIV) during COVID-19 and respect the “shelter at home” state-wide order this aim will be performed 100% virtually. The protocol specifically has been adapted to include

- 1) over the phone consent. This is a minimal risk study and with COVID-19 the risk of an in-person evaluation greatly outweighs the potential benefit.
- 2) Questionnaires to be completed via a) online through REDCAP mechanism that provides a link and password to allow participants to securely complete questionnaires or b) complete paper questionnaire mailed to participant with stamped envelope for return with only the study ID on papers to protect participant privacy
- 3) Online group meetings using Zoom with password to prevent hackers.
- 4) Compensation provided either using an electronic gift card or a script mailed to the study participant.

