Telephone or in Person Feedback from Each Session

Within 48 hours of the session each participant will be contacted by [name] or another trained member of the study team and will inquire about the experience of each individual. This will include aspects of the class they liked most and least. These surveys will also employ open-ended questions about program content.

Long-Term Follow Up

Each participant will be contacted via telephone 3, and 6 months after completion of the group ACT sessions by [name] or another trained member of the study team and will inquire about persistence of ACT practices and strategies participants recommend for ongoing use of ACT. Specifically we will ask if they are continuing ACT practices.

Step 2 Adapted ACT RCT

Screening Assessment (Week 0)

Screening will be identical to Step 1.

Entry Evaluations and Randomization

Subjects will be randomized (1:1) to ACT versus education control. A total of 20 subjects (10 per arm) will be randomized and followed for the duration of the six weeks of the intervention and control. Once ten participants are enrolled into one group that will start that adapted ACT intervention will start. At study entry baseline surveys will be collected using paper CRF or web-based computer assisted system (to view baseline survey see Appendix III) similar to Step 1.

On-Study Evaluations

Study specific follow-up visits for each subject will be kept to a minimum in order not to bias the outcome of lost to follow up. Participants will undergo pain and acceptability questionnaires at week 3 (Appendix VI). These will be repeated along with psychosocial co-morbidity questionnaires at week 8. Participants

will be provided \$20 for completion of baseline assessments, \$30 for midpoint and \$50 for endpoint assessments.

Instructions for Evaluations

Documentation of HIV

Documentation of HIV-1 infection will be confirmed by reviewing a positive test from any licensed screening antibody test, such as ELISA, and confirmed by a second antibody test, such as Western blot, or detectable plasma HIV-1 RNA at any time prior to study entry. If an ELISA or Western Blot is not available, HIV infection may be documented by two HIV RNA values \geq 2000 copies/mL, drawn at least 24 hours apart. The RNA assays should have been run at CLIA approved laboratory or equivalent.

Medical and Laboratory History

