If patients have had an antiretroviral resistance test during routine care, that data will be collected via chart abstraction.

Clinical Management Issues

This is a minimal risk study. No toxicities are anticipated a no treatment or invasive procedures are being performed as part of the study. However possible risks include:

Emotional distress

This behavioral intervention bring up past trauma or experiences that cause emotional distress. A highly experienced psychologist with post traumatic stress disorder experience is the Co-investigator of this study and will assist in triage as needed. In addition, the Owen Clinic has embedded psychiatrists that are available daily for emergency evaluations and will be utilized if any study personnel raise concerns about the state of participants. Emergency room evaluations will be encouraged if distress occurs after hours. Of note the AntiViral Research Center has a 24 hour physician on call to assist with triage of participants in various studies.

Selected Pain Interview

Participants will be asked to complete a short survey concerning their pain and pain treatment methods. These surveys will take place during the second (2nd) Arm 2 study visit.

Criteria for Discontinuation

- Subject requests to withdraw participation
- Primary care provider requests for subject withdrawal based on the provider's belief that study participation is no longer in subject's best interest
- Medical provider belief that the patient has life threatening clinical condition
- By the discretion of the site IRB, NIH or investigator

Statistical Considerations

This section briefly describes the planned statistical analysis. The statistical Analysis Plan (SAP) provides details. If the language in this section differs from the language in the SAP, the SAP takes precedence.

Analytic Plan: [name] and her team will lead all statistical analyses for this study. For the RCT we will obtain descriptive statistics to compare baseline characteristics between study arms (ACT versus pain education). Categorical variables will be analyzed using Fisher's Exact Test and continuous variables using Wilcoxon Rank Sum Test. To determine acceptability of group ACT, we will use the CSQ at endpoint of the intervention as the primary outcome. This is a pilot study, but we will utilize a superiority

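### The randomisation text for the pilot RCT gives 20 participants, but the Aims and the Aim 3 methods give 40; the recruitment target of 50 fits 40 and not 20

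*Combined protocol and SAP*

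**What the plan says.** Three places in the combined protocol and SAP give the size of the randomised comparison.

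- Section 6, Specific Aims, Aim 3: "Forty aPLWH with chronic non-cancer pain will be randomized to 6 weeks of group ACT or group education".
- Section 9, Aim 3 methods: "Forty persons will be randomized to either group adapted ACT or group education". The next sentence sets the recruitment target: "In anticipation of ~15% early discontinuation or lost to follow up, we plan to recruit 50 participants overall". The same paragraph describes delivery of adapted ACT in "weekly 2-hour group (8-10 persons per group) sessions for the 6 weeks of the intervention", and gives the education groups the same size range.
- Section 9, Step 2, Entry Evaluations and Randomization: "A total of 20 subjects (10 per arm) will be randomized". The sentence before it sets 1:1 allocation to ACT or education. The sentence after it concerns when a group begins: "Once ten participants are enrolled into one group that will start that adapted ACT intervention will start".

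The uncontrolled Aim 2 phase has its own sample: "Ten aPLWH will be recruited for 6 weeks of 2-hour group ACT".

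Section 9, Statistical Considerations, specifies an intent-to-treat approach with the endpoint CSQ as primary outcome. It gives no sample size, power, effect size or precision target. It contains a precedence rule: "If the language in this section differs from the language in the SAP, the SAP takes precedence".

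**The concern.** All three statements concern the same two-arm randomised comparison, and all three speak of participants being randomised. They differ by a factor of two. The smaller figure stands in the procedural text that staff would follow when allocating participants.

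The precedence rule does not settle the matter. It applies to the Statistical Considerations section, which gives no sample size, and the sentence with 20 lies outside that section. The supplied text has no separate SAP statement of sample size to defer to.

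What is at stake is the intent-to-treat denominator, the number of treatment groups in each arm, and the precision of the arm comparison on the CSQ. With one group per arm, the effect of the arm could not be separated from the effect of that one group and its leaders.

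A related gap lies in the Aim 3 paragraph. It calls 40 the number randomised, yet justifies recruiting 50 by discontinuation and loss to follow-up, which normally occur after randomisation. It is therefore unclear whether 40 is counted before or after loss.

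**Working it through.** **Inputs**

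- Randomised: 40 (section 6, Aim 3; section 9, Aim 3 methods) or 20 (section 9, Step 2).
- Loss allowance about 15%, recruitment target 50, group size 8–10 (section 9, Aim 3 methods).
- Allocation 1:1 (section 9, Step 2).
- Aim 2 sample 10 (section 9, Aim 2).

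**Step 1. Reproduce the target of 50.** Number to recruit = n / (1 − loss), rounded up.

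| Base n | n / 0.85 | Rounded up | Loss implied by recruiting 50 (1 − n/50) |
|---|---|---|---|
| 40 | 47.06 | 48 | 20% |
| 20 | 23.53 | 24 | 60% |

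From 40, the target is reproduced approximately: 48, stated as 50. The cruder formula n × 1.15 gives 46 from 40 and 23 from 20. No version brings 20 near 50.

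**Step 2. Check another meaning of the target.** If 50 covers Aims 2 and 3 together, 10 + 40 = 50, while 10 + 20 = 30. This does not favour 20 either, but it carries little weight (see the objection).

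**Step 3. Is 40 counted before or after loss?** Dividing 40 by 0.85 treats 40 as the number left after loss, whereas the text calls 40 the number randomised. The two readings give different trials:

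| Reading | Randomised | Per arm | Expected with endpoint data at 15% loss | Groups of 8–10 per arm |
|---|---|---|---|---|
| 40 is the randomised total | 40 | 20 | 40 × 0.85 = 34 | 2 |
| About 40 are to remain after loss | 48–50 | 24–25 | 50 × 0.85 = 42.5, about 42 (48 × 0.85 = 40.8) | 3 |
| Step 2 taken literally | 20 | 10 | 20 × 0.85 = 17 | 1 |

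Against 40, the Step 2 figure halves the intent-to-treat set (20/40 = 50%). Against 48–50, it removes 58–60% (1 − 20/48 = 58%; 1 − 20/50 = 60%).

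**Step 4. Precision, as an illustration only.** The plan states no SD or target difference, so work in SD units for a simple two-sample mean difference, without loss, covariates or clustering by group. Half-width = t(0.975, 2m − 2) × √(2/m), with m per arm.

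- m = 20: 2.024 × √0.10 = 0.64 SD.
- m = 10: 2.101 × √0.20 = 0.94 SD.
- Ratio: 0.94 / 0.64 = 1.47.

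**The case against.** The strongest defence is that 20 describes one wave: one ACT group and one education group of ten, run twice to reach 40. The group size of 8–10 is compatible with this, and so is the sentence about starting once ten are enrolled. Figure 2, the study schema, is not visible in the supplied text and could carry group numbers. This stands as a possibility. Against it, the sentence presents 20 as a total, and no supplied passage mentions waves or a second round. If the wave reading is right, the sentence still needs to say so.

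A second objection concerns the arithmetic on 50. The fit to 40 is approximate: 15% loss gives 48, and exactly 50 corresponds to 20%. The sum 10 + 40 = 50 is weak evidence, because the Aim 3 paragraph gives loss as the reason for 50 and that sum leaves no allowance for loss. Both points are fair, but neither helps 20.

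Third, this is an acceptability pilot with no stated power or precision goal, and the confidence interval calculation is not the logistic regression named in Statistical Considerations. That is correct. A reader might infer that the trial would fall short of its planned power at 20. The documents do not support that inference, because they plan no power.

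**Conclusion.** The contradiction is real and should be resolved. The supplied text carries two randomisation totals for one trial and no rule for choosing between them. Two explicit statements and the recruitment target favour 40, so the Step 2 sentence is the outlier. This rests on reading 50 as an allowance for loss, as the Aim 3 paragraph says, and on the supplied text alone.

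The consequence of following Step 2 literally is an intent-to-treat set at most half the size stated elsewhere, and one treatment group per arm. The widening of the interval from 0.64 to 0.94 SD shows the scale of the loss under simple assumptions; it breaches no documented target.

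A reader might go further and infer that 40 randomised, about 34 with endpoint data and two groups per arm are settled. They are not. Those figures take 40 as counted before loss, while the derivation of about 50 takes it as counted after loss. Using both applies the 15% twice. The Aim 3 paragraph leaves the choice open, and only the sponsor can make it.

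**What to change.** 1. Have the sponsor confirm the randomised total. Then correct the sentence in Step 2, Entry Evaluations and Randomization, to agree with section 6 and the Aim 3 methods: 40 in total, 20 per arm. If 20 is one of two waves, say so there and give the total as 40.
2. In the Aim 3 methods, state whether 40 is the number randomised or the number expected to have endpoint data after about 15% loss. Give the numbers consented, randomised and expected at endpoint separately: about 34 at endpoint if 40 are randomised, about 42 if 50 are. Say whether 50 includes the ten Aim 2 participants.
3. Make the target of 50 and the number of groups per arm consistent with that choice. If 48–50 are to be randomised, carry that figure into section 6 and Step 2 as well.

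If 40 is the randomised total, the cost is protocol wording. If 48–50 are to be randomised so that about 40 remain, each arm has 24–25 participants and needs three groups of 8–10. That is more delivery than two groups per arm, and the protocol should state it.

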study design, and incorporate an intent-to-treat (ITT) approach to analyze the outcome data. We will employ multivariable logistic regression analysis to study the association between clinical (duration of HIV infection, nadir CD4, BPI), demographic (i.e., age, sex, duration of HIV infection, nadir CD4), and psychosocial factors (i.e., substance use, loneliness) and intervention arm adjusting for baseline demographic and clinical characteristics. Variables significantly associated with treatment groups and outcome ($p < 0.10$) including appropriate interaction terms, will be included in the final multivariable logistic regression model as covariates. CSQ at midpoint and proportion of sessions attended will be evaluated in sensitivity analyses. The study procedures can occur in person or remotely. We will statistically evaluate this process and compare group cohesion scores between persons who attend live (if feasible) and remotely.

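### The statistical section clearly intends a between-arm comparison of endpoint CSQ but ties no test, model or effect measure to it; the only model stated relates patient factors to trial arm

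*Combined protocol and SAP*

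**What the plan says.** Section 9, under Statistical Considerations, calls itself a brief description and gives precedence to a SAP. The combined document contains no further SAP text. The Analytic Plan then says, in order:

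- Baseline characteristics are compared between arms. The next sentence names Fisher's exact test for categorical variables and the Wilcoxon rank-sum test for continuous ones.
- For acceptability, "we will use the CSQ at endpoint of the intervention as the primary outcome".
- The design is superiority, and the trial will "incorporate an intent-to-treat (ITT) approach to analyze the outcome data".
- The model sentence opens "We will employ multivariable logistic regression analysis to study the association between clinical (duration of HIV infection, nadir CD4, BPI), demographic". Its demographic list reads "demographic (i.e., age, sex, duration of HIV infection, nadir CD4", and it closes "i.e., substance use, loneliness) and intervention arm adjusting for baseline demographic and clinical characteristics".
- "Variables significantly associated with treatment groups and outcome" at p<0.10, with interaction terms, "will be included in the final multivariable logistic regression model as covariates".
- The last statement that mentions CSQ is this one: "CSQ at midpoint and proportion of sessions attended will be evaluated in sensitivity analyses".

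Elsewhere, the design overview at the start of section 9 describes the randomised trial as evaluating acceptability of adapted ACT against pain education.

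**The concern.** The trial's question is whether CSQ differs between arms. The one model described puts arm on one side and patient factors on the other, and CSQ is not in the sentence. Duration of HIV infection and nadir CD4 are listed as both clinical and demographic factors, and the model is then adjusted for baseline demographic and clinical characteristics, so the sentence cannot be carried out as written.

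If the SAP does not settle the matter, the form of the outcome, the model, the effect measure and the covariates are chosen after the data are seen. Two analysts working from this text could report different primary results. The sensitivity analysis of midpoint CSQ would also have no defined primary analysis to be compared with.

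**Working it through.** **1. The plan's own figures.** No significance level for the primary comparison, power, effect size or SD is stated for CSQ, so there is no primary-analysis figure to reproduce. The one design figure is the recruitment target under Aim 3: 40/(1 − 0.15) = 47.06, rounded up to 48, against 50 stated. It agrees within two participants and has no bearing on this point.

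**2. The statements side by side.**

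| Statement | CSQ named | Arms compared | Method named |
|---|---|---|---|
| Fisher / Wilcoxon | no | yes, at baseline | yes |
| Primary outcome | yes | implied | no |
| Superiority and ITT | no | implied | no |
| Logistic model | no | arm against patient factors | yes |
| Final logistic model | no (an unnamed outcome) | unclear | yes |
| Sensitivity analyses | yes, midpoint | not stated | no |

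No row has all three. The only other comparison stated is group cohesion, live against remote.

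**3. Model read literally.** logit P(arm = ACT) = β₀ + β′X, where X holds seven distinct factors: HIV duration, nadir CD4, BPI, age, sex, substance use and loneliness. CSQ does not enter, so its difference cannot affect the fit. A simulation (20 per arm, 1,000 replicates, true CSQ effects of 0, 0.5 and 0.9 SD) confirms this. The model's overall test rejected in 10.7%, 9.7% and 12.1% of replicates, with no trend. A direct Wilcoxon comparison of CSQ rejected in 4.6%, 32.2% and 77.6%.

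Age, sex, HIV duration and nadir CD4 are fixed before randomisation, so any association with arm is chance. With four independent factors, the probability that at least one reaches p<0.05 is 1 − 0.95⁴ = 19%. BPI, loneliness and substance use belong to the pain and psychosocial assessments, which Step 2 repeats after baseline. Only if baseline values are meant does the calculation extend to all seven: 1 − 0.95⁷ = 30%.

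**4. Model read with CSQ as outcome.** The covariate sentence mentions an outcome, and midpoint CSQ is a sensitivity analysis, so this may be the intent. A logistic model then needs a CSQ cut-point or an ordinal form. The section gives neither.

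**5. Wilcoxon read as covering CSQ.** The sentence follows the baseline comparison and precedes the first mention of CSQ in the Analytic Plan. If it does cover CSQ, there is a valid test but no effect estimate.

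**6. Illustration.** Assumptions not in the documents: normal score, 0.8 SD effect, two-sided 0.05, independent participants. With 20 per arm (Aim 3), the normal approximation for a difference in means is Φ(0.8·√(20/2) − 1.96) = Φ(0.57) = 0.716. Simulation gives (100,000 replicates; 3,000 for ordinal logistic):

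| Analysis | Power |
|---|---|
| t test | 69.3% |
| Wilcoxon | 66.9% |
| Ordinal logistic, 5 or 10 bands | 67.2%, 69.1% |
| Logistic after a median split | 40.6% |

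The median-split test has exact size 2.56%, and a t test at that size has 58.4% power. Of the 28.7 points lost, 69.3 − 58.4 = 10.9 come from the smaller size and 58.4 − 40.6 = 17.8 from dichotomising. Over 0.5 to 1.0 SD, power is 34–87% (t), 32–85% (Wilcoxon) and 16–60% (median split). With 10 per arm (Step 2) and 0.8 SD it is 40%, 35% and 19%.

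**7. Screening.** With a median split, power was 40.3% with p<0.10 screening and 41.1% without (4,000 replicates). The objection to screening is that the data choose the model; the effect on power is small.

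**8. Group delivery.** Both arms meet in groups of 8–10, so 20 per arm means 20/10 = 2 to 20/8 = 2.5 groups per arm. With within-group correlation ρ, the variance of an arm mean rises by 1 + (m − 1)ρ, that is 1 + 7ρ to 1 + 9ρ. The documents give no ρ, and the figures in step 6 take it as zero.

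**The case against.** The strongest reply is that the governing text is not available: the section is a summary, and trial analysts would follow the SAP. That stands as a limit. A reader might infer that the trial has no primary analysis. The documents do not support this, because a SAP is cited and the superiority and ITT wording, with the stated purpose of the trial, shows that a between-arm comparison is intended. What is missing here is its method. Even so, a summary should not describe a different model from the one that answers the question.

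The Wilcoxon sentence is general in its grammar and could be extended to CSQ. That reading costs almost no power, as step 6 shows, but it leaves the pilot without an estimate and leaves the logistic sentence unexplained.

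A reader might also infer that all seven factor–arm associations are null by randomisation. That is certain only for the four fixed beforehand. The plan does not say whether BPI, loneliness and substance use are baseline values, and later values could differ by arm because of treatment. Such a model still would not estimate a CSQ difference.

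Finally, a reader might infer that CSQ will be dichotomised, with the power loss shown. No split appears in the documents. The 41% shows what one possible repair of the sentence would cost; it is not a property of the plan.

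**Conclusion.** The point holds for the text available: endpoint CSQ is the primary outcome, a comparison between arms is intended, and no test, model or effect measure is attached to it. The stated logistic model does not estimate that difference at any effect size, and this conclusion rests on the wording alone.

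The power figures are illustrations under the assumptions in step 6. They show that the choice between a t test and Wilcoxon hardly matters (69% against 67%) and that a material loss arises only under a split the plan never mentions. For a pilot without a power target, the main loss is a clear, pre-set estimate of the CSQ difference. The section should be corrected, but the point does not put the design itself in doubt.

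**What to change.** Replace the logistic sentence, as the primary analysis, with: *Endpoint CSQ score is compared between randomised arms (ITT) by linear regression on arm, with the mean difference and 95% CI; the Wilcoxon rank-sum test with the Hodges-Lehmann estimate is the sensitivity analysis.* Linear regression is one reasonable choice; what matters is that the method is fixed in advance and yields an estimate.

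- If adjustment is wanted, name one or two covariates now. Delete the p<0.10 screening and the unspecified interactions from the primary model. The logistic or association model may stay, labelled exploratory.
- Because both arms are delivered in groups, add a sensitivity analysis that widens the interval over a stated range of within-group correlation, and report that the small number of groups limits the inference.
- If the SAP already specifies a CSQ model, align this section with it.
- Separately, reconcile the number randomised (40 under Aim 3, 20 under Step 2, Entry Evaluations and Randomization) and the endpoint week (week 6 under Aim 3, week 8 under On-Study Evaluations).

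The cost is analysis-plan wording only, since the variables are already collected. The one downside is a wider interval in the group-delivery sensitivity analysis.

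### The planned logistic analysis sets no limit on terms and no CSQ cut-off; with about 40 people it is unreliable if all seven named factors, or screened interactions, are fitted

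*Combined protocol and SAP*

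**What the plan says.** The Analytic Plan (Section 9, Statistical Considerations) makes the CSQ at the end of the intervention the primary outcome and declares a superiority design with an intent-to-treat analysis. The modelling sentence begins "We will employ multivariable logistic regression analysis to study the association between clinical (duration of HIV infection, nadir CD4, BPI), demographic". The full list reads "duration of HIV infection, nadir CD4, BPI), demographic (i.e., age, sex, duration of HIV infection, nadir CD4), and psychosocial factors (i.e., substance use, loneliness". Two factors appear twice, which leaves seven: HIV duration, nadir CD4, BPI, age, sex, substance use and loneliness. Intervention arm and adjustment for baseline characteristics are added.

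A second sentence describes selection: "Variables significantly associated with treatment groups and outcome ($p < 0.10$) including appropriate interaction terms, will be included in the final" model. No maximum number of terms, named test, penalised or exact method, or rule for a non-converging fit is given. The CSQ has no cut-off, although logistic regression needs a binary outcome.

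On sample size, the Aim 3 text in Section 9 states "Forty persons will be randomized to either group adapted ACT or group education" and "In anticipation of ~15% early discontinuation or lost to follow up, we plan to recruit 50 participants overall". The Step 2 text on entry and randomization states "A total of 20 subjects (10 per arm) will be randomized".

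**The concern.** Seven factors plus arm make eight coefficients before any interaction. An even split of 34 to 40 people gives 17 to 20 events, or roughly two per coefficient, and fewer if most participants are satisfied. With so few events, maximum-likelihood logistic regression tends to push odds ratios away from 1. It can also fail to give a finite estimate (separation), and its likelihood-ratio and Wald tests can disagree.

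The same data could therefore give an inflated ACT odds ratio, a failed fit or an ordinary result. Which one occurs would depend on choices the plan leaves open: the cut-off, the test, how the screen is read, and which interactions count as appropriate. This affects the primary outcome of a comparison declared as superiority.

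**Working it through.** **Sample size.** The one planning figure that can be checked is the recruitment target. 40 / (1 − 0.15) = 47.1, or 48 with equal arms, close to the stated 50. The number with an endpoint is then:

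- 40, if 40 is the target after loss;
- 50 × 0.85 = 42.5, if all 50 are randomised;
- 40 × 0.85 = 34, if the loss falls on the 40 randomised;
- 20 or fewer, on the Step 2 text.

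**Events per coefficient, arm + 7.** At 50% satisfied: 17/8 = 2.1 (n = 34) to 20/8 = 2.5 (n = 40). At 80% satisfied the smaller class has 6.8 to 8 people, so 6.8/8 = 0.85 to 8/8 = 1.0.

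**Simulation.** Inputs from the documents: 1:1 allocation; 28% women and 75% with a substance use history (Section 10). Assumptions, because the plan gives no value: event rate 50%, 70% or 80%; five normal covariates; three covariates with log-odds ratio 0.4 per SD; arm odds ratio (OR) 1 or 3; two-sided 5% test. There were 2,000 trials per setting, or 800 where interactions were screened. The Monte Carlo standard error near 10% is √(0.1 × 0.9/2000) = 0.7 points, or √(0.1 × 0.9/800) = 1.1 points. Separation was detected by linear programming. Results for n = 34 and 40, with the median OR taken over finite fits:

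| Model | No finite estimate | Likelihood-ratio rejection, OR = 1 | Median OR, true OR = 3 |
|---|---|---|---|
| Arm only | 0% (OR = 1) | 5.1–7.6% | – |
| Arm + all 7 | 2–5% (50% satisfied); 7–14% (70%); 19–36% (80%) | 9.0–14.9% | 4.1–4.9 |
| Arm + 7 + 2 arm interactions | 2–50% | 11–20% | 4.8–5.8 |
| Screened on arm and outcome, main effects only | 0–7% | 3.7–6.4% | 2.5–2.9 |
| Screened on outcome or on either, main effects only | 1–14% | 5.2–8.0% | 3.0–3.4 |
| Screened, arm interactions admitted at p<0.10 | 19–49% | 9–17% | 2.6–3.6 |

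In the arm + 7 model, the likelihood-ratio error is 9.0/5 = 1.8 to 14.9/5 = 3.0 times nominal. The OR is overstated by (4.1 − 3)/3 = 37% to (4.9 − 3)/3 = 63%. A Wald test in that model rejects 2–7%.

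**Other sizes, arm + 7.** At n = 43, 1–17% of fits fail and likelihood-ratio error is 8.5–11.8%. At n = 20, 51–83% fail and the error is 19–22%.

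**Why the main-effects screen helps.** If a variable must be associated with both arm and outcome, and neither association is real, the expected number entering is about 7 × 0.10 × 0.10 = 0.07. With the assumed real effects on outcome it is about 0.1. The looser screens admit 1.0–1.9 covariates.

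**Power.** For a 0.5 SD effect on the score, a linear model with arm and pre-named covariates held 4–5% error, always fitted, and had about 25–35% power. By Wald test, the logistic main-effects versions had about 11–20%, and those with screened interactions 7–14%.

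**The case against.** A reader might infer that the plan commits to an eight-coefficient model that often fails and doubles the false-positive rate. The documents do not support that, for four reasons.

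- The seven factors are candidates, and only those passing the screen enter the final model. Read literally and with main effects only, the screen admits almost none of them.
- The doubled error belongs to a likelihood-ratio test, which the plan does not name. Wald tests on the same full model are close to nominal or conservative.
- How often fits fail depends on an event rate the plan does not define. At 50% satisfied it is only 2–5% without interactions.
- Taking 15% off 40 is the harshest reading, because 50 are to be recruited to cover that loss.

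All four stand. They do not dispose of the point, because the screening rule expressly admits interactions. With those, failed fits and likelihood-ratio error return, though the median OR shows little inflation. The modelling sentence can also be read as a multivariable fit in its own right, before the final model.

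Three further objections deserve weight. The sentence can be parsed with arm as the dependent variable. The results for the ACT odds ratio would then not apply, and the sentence would give no model for the CSQ comparison. The power contrast changes outcome scale and model together (and, for the full model, the number of covariates), and it generates satisfaction from a continuous score, which favours the linear model. Finally, this is a pilot, and the section defers to an SAP for details; the combined document holds no further detail on this model.

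**Conclusion.** The concern holds as one of under-specification with a measurable consequence. At about 40 people, the analysis is unreliable if all seven factors are fitted with arm or if arm interactions are screened in, and nothing in the plan rules out either. With main-effects screening only, the likelihood-ratio error (3.7–8.0%) and the OR are close to target, and what remains is chiefly the power lost by dichotomising.

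The plan therefore cannot be said to produce an inflated result; whether it does depends on choices not yet written down. The sizes rest on the assumed event rates and covariate effects and on 34 to 43 people with an endpoint. If the Step 2 figure of 20 is the operative one, the full model is much worse. Confidence is medium. The wording should be settled before outcome data are analysed.

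**What to change.** Make the primary analysis a linear regression of the endpoint CSQ score on arm plus a small number of baseline covariates (for example two) named in advance. Remove the p<0.10 screen and the interaction terms from that model, and report the other factors descriptively.

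If a yes/no CSQ is kept, state the cut-off and use Firth-penalised logistic regression with the same covariate limit and penalised-likelihood intervals. State which variable is dependent, and reconcile 40 with 20 randomised.

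The cost is a change of wording in the analysis plan. The downside is that the many-factor association model becomes exploratory. The limit of two is a judgement rather than a threshold; the essential part is that the covariates are few and fixed beforehand.
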